7.2.2 Handling of Intercurrent Events

The expected intercurrent events (ICEs) of interest in this trial are:

[figure not shown]
- Treatment discontinuation
- Initiation of macrolides during trial
- Start of cyclic doses of antibiotic treatment during the trial
- Initiation or Change of CFTR-MT during the trial

For the primary objective, intercurrent events will be handled by using the while-on-treatment strategy, as defined in ICH E9(R1) [[R21-0743](#)]. Measurements, taken prior to the intercurrent event, will be used to assess treatment effect.

For the secondary objective, intercurrent events will be handled by using the treatment policy strategy, as defined in ICH E9(R1). Use of the “treatment policy” approach disregards the intercurrent event and uses measurements regardless of the occurrence of an intercurrent event. Additional details regarding intercurrent event handling strategy will be described in the TSAP.

7.2.3 Primary objective analyses

The primary endpoint as described in [Section 2.1.2](#), will be derived according to BI standards. The analysis will be based on the TS and will be descriptive in nature. The number and proportion of patients, with at least one TEAE per treatment group, will be derived. TEAE is defined as all adverse events occurring between the start of treatment and the end of the REP (see [Section 1.2](#)). Adverse events that start before first drug intake and deteriorate under treatment will also be considered as ‘treatment-emergent’.

7.2.4 Secondary objective analyses

7.2.4.1 Neutrophil elastase activity in sputum

The biomarker endpoint as described in [Section 2.1.3](#) will be analysed based on the TS. The analysis of this endpoint will be performed on log transformed data.

Baseline NE activity, in sputum, will be derived as the mean value of available valid samples of Screening and Week 0, prior to the first treatment intake. The change from baseline of NE activity, in sputum, at different visits (X) is calculated as:

[figure not shown]
Change from baseline in NE activity at Visit X = NE activity at Visit X – NE activity at Baseline

The change from baseline, in NE activity in sputum, at Week 8, will be analysed by descriptive statistics and graphical representations across all visits.

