Statistical methods	The primary endpoint and secondary endpoints will be evaluated using descriptive statistics. No confirmatory testing is performed and hence no null and alternative hypotheses are defined. All evaluations are to be considered exploratory.

FLOW CHART

Trial Periods	Screening	Treatment					End of study
Visit	1	2	3	4	5	6 / EoT ¹	7 / EoS ¹ / FU
Week	-6	0	1	4	8	12	16
Day	-42	1	8	29	57	85	113
Time window for visits [days]	≥7 d prior V2	-	±3	±3	±3	±3	+7
Informed consent ²	X						
Demographics	X						
Medical history / proof of CFB diagnosis	X	X					
CT scan (proof of BE diagnosis) ³	X						
Review of in-/ exclusion criteria	X	X					
Physical examination including skin	X	X	X	X	X	X	X
Vital signs, pulse rate, blood pressure, aural body temperature ⁵	X	X	X	X	X	X	X
Height (only at Visit 1) / body weight	X	X				X	
Sputum collection at site (spontaneous or induced) ⁶	X	X		X	X	X	X
Sputum collected at home (backup sample, if needed) ⁷		(X)		X	X	X	X
P. aeruginosa sputum sample for culture ⁸	X					X	
Murray sputum colour chart	X	X					
12-lead ECG	X	X		X		X	
Panoramic radiography ¹¹	X						
Safety laboratory tests (blood / urine samples) ¹²	X	X	X	X	X	X	(X)
Pregnancy tests ¹³	X	X		X	X	X	X
Cotinine (urine)	X	X		X	X	X	X
PK blood sample (profile) ¹⁵		X				X	
PK blood sample (trough) ¹⁵		X	X	X	X	X	

Trial Periods	Screening	Treatment						End of study
Visit	1	2	3	4	5	6 / EoT ¹		7 / EoS ¹ / FU
Week	-6	0	1	4	8	12		16
Day	-42	1	8	29	57	85		113
Time window for visits [days]	≥7 d prior V2	-	±3	±3	±3	±3		+7
[REDACTED]								
All AEs/SAEs/AESIs; concomitant therapy	X	X	X	X	X	X		X
Pulmonary exacerbation review, eCRF documentation		X	X	X	X	X		X
IRT call/notification	X ¹⁸	X		X	X	X		
Randomisation		X ¹⁹						
Dispense trial medication ²⁰		X		X	X			
Collect trial medication				X	X	X		
Compliance / drug accountability				X	X	X		
Completion of trial participant participation								X

- 1 Patients who completed treatment as planned will have an End of Treatment Visit (EOT) and a subsequent Follow up Visit after 28 (+7) days. The Follow-up Visit will be End of Study (EOS). Trial participants who discontinue trial treatment prematurely should undergo the EOT Visit as soon as possible and the EOS Visit 28 (+7) days thereafter.
- 2 Informed consent needs to be signed before any trial-related procedure is performed (before or at Visit 1).

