2. TRIAL OBJECTIVES AND ENDPOINTS

2.1 MAIN OBJECTIVES, PRIMARY AND SECONDARY ENDPOINTS

2.1.1 Main objectives

The aim of the trial is to investigate whether 5 mg qd of BI 1291583 (the expected human therapeutic dose) in patients with CF is safe and to assess PD and PK. Based on these data, an across-trial comparison will be performed.

The primary objective, is to estimate the number and percentage of patients who have at least one treatment-emergent AE (TEAE) during the trial.

The secondary objective is to estimate the PD effect, at Week 8, after the first drug administration. The other secondary objective is to estimate the PK effect, after the first dose and at steady state, after multiple dosing of BI 1291583 5 mg qd.

All treatment effect estimations will be as randomised, including the effects of any changes of treatment.

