3.2 DISCUSSION OF TRIAL DESIGN, INCLUDING THE CHOICE OF CONTROL GROUP(S)

Since this trial evaluates BI 1291583 for 12 weeks and for the first time in a CF patient population, safety and tolerability is the primary objective. A randomised, double-blind, placebo-controlled, parallel group trial is considered the most robust design to assess safety, tolerability, pharmacodynamic and pharmacokinetics of BI 1291583. A double-blind concept was chosen to reduce the bias with regards to treatment-dependent effects as much as possible. Due to a close safety monitoring and the fact that no SoC treatments are restricted, this approach is considered acceptable for patients. A placebo group is included in order to reduce bias and to provide a comparator arm to reliably assess safety, tolerability, and pharmacodynamic effects of the trial medication.

Availability of clinical safety, efficacy and surrogate biomarker (i.e. free NE activity) data in a patient population with BE not related to CF [[c35703911-05](#)] are considered sufficient to evaluate their similarity in CF patients with BE. Detection of early signs of clinical efficacy and safety of BI 1291583 are expected over a 12-week treatment period.

Evaluation of NE inhibition at Week 8 (secondary endpoint) takes into account potential effects of maintenance cycling antibiotic treatment.

Before initiating future trials including CF and NCF patients with BE within one study, the data from [REDACTED] and 1397-0013 (CFB) will be reviewed ([Figure 3.2: 1](#)).

Although there is no evidence that genetic defects causing CF directly lead to altered pharmacokinetics, differences in the PK of CFB patients compared to healthy volunteers could result from pathophysiological differences in the gastrointestinal tract which may impact absorption. In addition, higher volume of distribution and clearance were observed in CF patients potentially related to an altered body composition [[R22-1342](#)]. Deficiency of functional CFTR in CF leads to decreased ductal cell secretions of Cl⁻, water and HCO3⁻, which also lowers pH [[R22-2965](#), [R22-2966](#)].

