### **% inhibition analyses**

The assessment of NE activity will further comprise the analysis of the % inhibition of NE activity. For the purpose of descriptive analysis, for each time point including baseline, % inhibition will be calculated as:

$$NE \ inhibition_t = \frac{NE \ activity_{baseline} - NE \ activity_t}{NE \ activity_{baseline}} \times 100$$

Descriptive statistics for absolute % inhibition by timepoint and treatment group will be presented. Maximum % inhibition (on patient level during the trial) will be summarized by treatment group. The median % inhibition of NE activity per treatment group over time will be plotted. All timepoints will be taken into account, analysis windows will be applied to the % inhibition of NE activity.

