### **Change from baseline analyses**

Change from baseline in log10-transformed NE activity in sputum up to Week 12 after first drug administration will be analysed by descriptive statistics and graphical representations across all visits. Descriptive statistics of change from baseline will be presented by timepoint and treatment group.

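### No placebo-adjusted estimate with a confidence interval is specified, in the readable text, for Week 8 sputum NE activity

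*Protocol*

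**What the plan says.** **Purpose.** Protocol 2.1.1 states: "The secondary objective is to estimate the PD effect, at Week 8, after the first drug administration". Protocol 3.2 says placebo is there to "provide a comparator arm to reliably assess safety, tolerability, and pharmacodynamic effects of the trial medication". Protocol 7.4 stratifies randomisation by CFTR-MT (yes/no) at 2:1. Protocol 7.5 plans 16 active and 8 placebo patients and names sputum NE inhibition as a main interest for development decisions.

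**Analysis.** The synopsis says: "The primary endpoint and secondary endpoints will be evaluated using descriptive statistics". Under Protocol 7.2.4.1, the Week 8 change from baseline in NE "will be analysed by descriptive statistics and graphical representations across all visits". On baseline, the same section says: "Baseline NE activity, in sputum, will be derived as the mean value of available valid samples of Screening and Week 0". The SAP's change-from-baseline paragraph says: "Descriptive statistics of change from baseline will be presented by timepoint and treatment group". Its % inhibition paragraph divides by baseline and adds: "The median % inhibition of NE activity per treatment group over time will be plotted".

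**What is not stated.** No readable text for this endpoint gives an active/placebo difference or ratio, a confidence interval, a baseline covariate or a CFTR-MT term. SAP 5.2.2.1 says the relative change at Week 8 will be estimated and points to 7.5.2.1, where only descriptive output can be read.

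**The concern.** A change within the active arm contains the drug effect plus anything else that moves NE over eight weeks. The protocol itself expects cycling antibiotics to matter, since Week 8 was chosen with that in mind (2.1.3 and 3.2). Regression to the mean is also possible. The placebo contrast is what separates these from the drug effect, and it is the quantity that the objective and the stated role of placebo call for. Without it, the treatment-policy strategy set for this objective (Protocol 7.2.2, SAP 6.3) has no between-arm summary measure attached. Readers who use NE for development decisions would see two columns of summaries and no statement of how uncertain the difference between them is.

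**Working it through.** **1. The plan's own figure.** Protocol Table 7.5: 1 gives a 64.7% chance of observing at least an 80% reduction with 16 active patients and a true 90% reduction.
- Method: draw 16 log10 ratios from a normal distribution with mean log10(0.10) = −1 and SD 2.15, and take the median % reduction in the active arm.
- Result: 65.0% over 100,000 runs. Within 2 points, 53 of the table's 54 cells agree. The exception is n = 24, true 95%, at least 90%: stated 80.3%, computed about 69.7%.
- A two-arm difference in mean log10 at 16:8 gives 62.7% for this cell, and using 8 placebo patients throughout matches only 7 of 54 cells. The sample-size rationale is therefore also built on the active arm alone.

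**2. Effect of background change.** The documents give no placebo change, so 20–50% is an assumption.
- Within-arm reading = 1 − (1 − true)(1 − drift).
- True 80%: drift 20%, 30%, 50% gives 1 − 0.2 × 0.8 = 84%, 1 − 0.2 × 0.7 = 86%, 1 − 0.2 × 0.5 = 90%.
- No drug effect: 20%, 30%, 50%.

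**3. Precision of the placebo contrast.** Inputs: SD 2.15 log10 and 16 versus 8 (Protocol 7.5). The protocol does not say whether 2.15 is the SD of the change or of the level; it is taken here as the SD of the analysed quantity.
- SE = 2.15 × √(1/16 + 1/8) = 0.931.
- 95% half-width = 2.074 (t, 22 df) × 0.931 = 1.93 log10, a factor of 10^1.93 ≈ 85 each way.
- An estimated 90% reduction (ratio 0.10) would have a ratio CI of about 0.0012 to 8.5.
- With 12 versus 6 evaluable (the 6 is assumed): SE 1.075, half-width 2.28 log10, factor about 190.

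**4. Gain from baseline as a covariate.** Take unit variance, within-patient correlation (ICC) ρ, and baseline as the mean of two samples.
- Change-score variance: 1 + (1 + ρ)/2 − 2ρ = 1.5(1 − ρ).
- ANCOVA residual variance: 1 − 2ρ²/(1 + ρ), times 1 + 1/(24 − 4) = 1.05 for estimating the slope with 24 patients.

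| ICC (assumed) | ANCOVA × 1.05 | Change score | Ratio |
|---|---|---|---|
| 0.2 | 0.980 | 1.20 | 0.82 |
| 0.4 | 0.810 | 0.90 | 0.90 |
| 0.5 | 0.700 | 0.75 | 0.93 |
| 0.6 | 0.578 | 0.60 | 0.96 |
| 0.8 | 0.303 | 0.30 | 1.01 |

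Simulation agrees within about a point. The gain is about 18–19%, 9–10%, 7%, 3–4% and none. The documents give no ICC.

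**The case against.** **The placebo arm and the baseline are used.** A reader might infer that both are ignored. The documents do not support that. Placebo is tabulated and plotted beside active, and baseline is the subtrahend of the change score and the denominator of % inhibition. What is absent is the contrast, the interval, and baseline as a covariate.

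**A model may exist in removed text.** The SAP abbreviations list ANCOVA, MMRM, REML and AIC, and the protocol lists MMRM and REML. No readable analysis uses them. The SAP contents place 7.5.2.1 on page 22 and 7.5.2.2 on page 24, so there is room for more text. This stands: absence can be claimed only for what is readable. The terms also sit in a list with hazard ratio and Kaplan-Meier, so they may serve other endpoints, and the readable synopsis and 7.2.4.1 say descriptive.

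**Descriptive reporting is a disclosed choice.** The trial is exploratory, is not sized by power, and aims at a comparison with the non-CF bronchiectasis trial. Means, SDs and counts by arm would let a reader compute the unadjusted ratio. That explains why there is no test. It does not explain why the estimate named in the objective is left to the reader, and Protocol 7.1 leaves room for exploratory intervals.

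**The contrast is noisier than the active arm alone.** This is the strongest point. If 2.15 is the SD of change, the active-arm mean has SE 2.15/√16 = 0.54. A 30% placebo fall is a bias of 0.155 log10, giving RMSE √(0.54² + 0.155²) = 0.56; a 50% fall gives 0.62. The unadjusted contrast has 0.93. The contrast wins on RMSE only if the drift exceeds SD/√8, which is 0.76 log10 (a fall of about 83%) at SD 2.15. For a 30% or 50% fall, the SD would have to be below about 0.44 or 0.85. So the model should not be sold as a more accurate number at the planned SD. It answers the stated question and shows its uncertainty, which summaries by arm do not.

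**Conclusion.** The point holds for the readable text: the objective and the role given to placebo call for a between-arm estimate at Week 8, and none is specified. It is a low-cost improvement, not a flaw that undermines the trial; no primary conclusion, sample size or stated decision rule changes.

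The size rests on assumptions. The 84–90% reading of a true 80% reduction depends on a placebo fall of 20–50%, which has no source in the documents. Regression to the mean is possible but not established, since the readable entry criteria do not select on high NE. The variance gain from adjustment is modest and depends on an unknown ICC. The interval factor of about 85 depends on SD 2.15 applying to the analysed quantity and on all 24 patients being evaluable.

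A reader might also infer that a model would deliver a usable effect size. At the planned SD it would not. Its value is a correctly defined contrast with its uncertainty in view.

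**What to change.** In SAP 7.5.2.1, pre-specify one exploratory Week 8 ANCOVA on log10 NE with treatment, log10 baseline NE and CFTR-MT stratum, or an MMRM over all visits with the same terms. Report the active/placebo ratio, back-transformed to % reduction, with a 95% CI, and label it exploratory. Keep the planned summaries and plots.

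State beside it that the interval is expected to be very wide at SD 2.15 log10 and that the gain over a change score is modest.

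If such a model already exists in removed text, no new analysis is needed; amend the synopsis and Protocol 7.2.4.1 to agree with it.

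Cost: one model, one table and two covariate degrees of freedom for the ANCOVA. No new patients, visits or samples.

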7.2.4.2 Pharmacokinetic endpoints

The PK parameters, described in [Section 2.1.3](#), will be estimated using a population PK modelling approach. The PK endpoints (concentrations and parameters) will be reported descriptively, based on the PKS. For all patients, the following descriptive statistics will be calculated for plasma concentrations and PK parameters: number (N), arithmetic mean, standard deviation, minimum, median, maximum, arithmetic coefficient of variation, geometric mean, and the geometric coefficient of variation. The following statistics will additionally be provided for PK parameters: the 10th, 25th, 75th, and 90th percentiles.

7.2.6 Safety analyses

All treated patients will be included in the safety analysis. In general, the safety analyses will be descriptive in nature and will be based on BI standards. No hypothesis testing is planned.

Adverse events will be coded using the Medical Dictionary for Drug Regulatory Activities (MedDRA). Standard BI summary tables and listings will be produced. All adverse events with an onset between the start of treatment and the end of the REP, a period of 28 days after the last dose of trial medication, will be assigned to the on-treatment period for evaluation.

Statistical analysis and reporting of AEs will concentrate on TEAEs (see [Section 7.2.3](#)).

Frequency, severity, and causal relationship of adverse events will be tabulated by system organ class and preferred term, after coding according to the current version of the Medical Dictionary for Drug Regulatory Activities (MedDRA), at database lock.

Laboratory data will be analysed both quantitatively as well as qualitatively. The latter will be done via comparison of laboratory data to their reference ranges. Values outside of the reference range, as well as values defined as clinically relevant, will be summarised.

Vital signs, physical examinations, or other safety-relevant data observed at screening, baseline, during the course of the trial, and at the end-of-trial evaluation, will be assessed with regard to possible changes compared with findings before start of treatment.

Clinically relevant abnormal findings of ECG will be reported and analysed as baseline conditions (at screening) or as AEs (during the trial).

7.2.7 Other Analyses

Other analyses are not planned.

7.2.8 Interim Analyses

Given the exploratory nature of this study, the sponsor may choose to conduct an interim PD/PK analysis [REDACTED]

[REDACTED]. The decision to conduct an optional interim analysis, and the timing of the analysis, will be documented in the sponsor's trial master file, in a logistics and access plan, prior to the conduct of the interim analysis. There is no plan to adjust sample size based on the interim analysis results. The interim analysis will be performed and interpreted, by an independent evaluation team of the sponsor, which is independent of the trial team. No interim report will be written.

To ensure patient's safety during the trial, a fully external DMC, independent of the trial and project teams, will review periodically all available safety data. A DMC SAP, which describes the analyses required for assessment by the DMC, will be produced. Further details will be provided in a DMC charter.

7.3 HANDLING OF MISSING DATA

In general, missing data will not be imputed.

Primary endpoint

Missing or incomplete AE dates will be handled according to BI standard.

Secondary PK endpoints

Handling of missing PK data will be performed according to the Sponsor's SOPs.

PK parameters, that cannot be reasonably calculated based on the available drug concentration-time data, will not be imputed.

7.4 RANDOMISATION

The randomisation will be stratified according to the use of SoC CFTR-MT (yes vs. no).

Within each stratum, patients will be randomised, in a 2:1 ratio, to either receive BI 1291583 5 mg qd, or placebo.

BI will arrange for the randomisation and the packaging and labelling of trial medication.

The randomisation list will be generated, using a validated system, which involves a pseudo-random number generator, so that the resulting treatment will be both reproducible and non-predictable. Specific parameters, used for the creation of the randomisation schedule (e.g. block size or biasing coin probabilities), will be documented in the CTR. Access to the codes will be controlled and documented.

7.5 DETERMINATION OF SAMPLE SIZE

For this exploratory trial, it is planned to include a total of 24 treated patients. Sixteen (16) patients will receive BI 1291583, 5 mg qd, and 8 patients will receive placebo. The planned sample size is not based on a power calculation but is considered sufficient, for the exploratory evaluation of safety, tolerability of BI 1291583, as well as to investigate PD and PK properties.

Apart from the safety assessment, NE inhibition, in sputum, is one of the main interests of the study to support further drug development decisions for BI 1291583. A variety of different effect sizes for % NE reduction were investigated, and [Table 7.5: 1](#) shows the simulated operating characteristics of the design for different scenarios and sample sizes for the active arm.

With 16 (24) patients in the active group, there is approximately 65% (70%) probability to observe a % reduction in NE activity, in sputum, of at least 80% when the true effect size is 90%. In contrast, if the true effect size is 40%, the probability to observe a % NE reduction of at least 80% would be 21%, for 16 patients in the active group, and 18% if there are 24 patients randomised, in the active group. If only 12 patients are evaluable for the assessment of % NE reduction at week 8 (e.g., due to dropouts) the increased uncertainty for a correct decision is considered acceptable.

Overall, a sample size of 16 patients, in the active group, is regarded as sufficient for the objectives of this trial.

Table 7.5: 1 Simulated probabilities for observing at least a given % reduction in NE activity, in sputum, at 8 weeks

Sample size	%Reduction	Probability to observe at least a 70% reduction (%)	Probability to observe at least an 80% reduction (%)	Probability to observe at least a 90% reduction (%)
12	95%	82.4%	75.5%	61.2%
	90%	70.0%	61.5%	45.4%
	80%	55.5%	45.7%	30.9%
	70%	45.7%	37.7%	22.6%
	50%	34.3%	25.9%	14.9%
	40%	30.1%	23.2%	12.4%
16	95%	86.9%	80.1%	64.2%
	90%	74.3%	64.7%	46.6%
	80%	57.7%	47.2%	29.5%
	70%	47.5%	36.7%	21.4%
	50%	34.4%	24.0%	12.8%
	40%	29.5%	21.1%	10.2%
24	95%	92.0%	86.0%	80.3%
	90%	80.3%	70.3%	48.4%
	80%	60.5%	47.9%	26.6%
	70%	47.8%	35.3%	17.3%
	50%	32.1%	21.2%	8.5%
	40%	26.8%	18.0%	6.9%

Assumptions: SD= 2.15 (on a log10 scale).

Simulations were performed using R Version 4.0.2, with 10000 simulation runs per scenario.

8. INFORMED CONSENT, TRIAL RECORDS, DATA PROTECTION, PUBLICATION POLICY, AND ADMINISTRATIVE STRUCTURE

The trial will be carried out in compliance with the protocol, the ethical principles laid down in the Declaration of Helsinki, in accordance with the ICH Harmonised Guideline for Good Clinical Practice (GCP), relevant BI Standard Operating Procedures (SOPs), the EU Regulation 536/2014 and other relevant regulations. Investigators and site staff must adhere to these principles. Deviation from the protocol, the principles of ICH GCP or applicable regulations will be treated as “protocol deviation”.

Standard medical care (prophylactic, diagnostic and therapeutic procedures) remains the responsibility of the treating physician of the trial participant.

The investigator will inform the sponsor or delegate immediately of any urgent safety measures taken to protect the trial participants against any immediate hazard, as well as of any serious breaches of the protocol or of ICH GCP.

The Boehringer Ingelheim transparency and publication policy can be found on the following web page: trials.boehringer-ingelheim.com. The rights of the investigator and of the sponsor with regard to publication of the results of this trial are described in the investigator contract. As a rule, no trial results should be published prior to finalisation of the CTR.

The certificate of insurance cover is made available to the investigator and the trial participants and is stored in the ISF.

